4.2.3 VORICONAZOLE COMPARATOR

Patients randomized to this regimen will start prophylaxis within 24 hours of transplant (Day 0). Continue prophylaxis until the occurrence of any of the following, whichever is sooner:

- Day +42
OR
- Day of Hospital Discharge
OR
- Patient meets any of the off protocol therapy criteria (Section 8.1)

If other systemic antifungal therapy is initiated for empiric therapy or treatment of suspected infection, then voriconazole prophylaxis should be held and voriconazole should resume when other systemic antifungal therapy is discontinued if this occurs prior to Day +42, Day of Hospital Discharge, or patient off protocol.

Following completion of study prophylaxis, institutions may revert to local standard of care for post-engraftment anti-fungal prophylaxis.

VORICONAZOLE: by slow IV infusion over 1-2 hours* (or longer) OR by mouth:

| Age | Weight | Loading dose* IV q12h x 2 doses | Maintenance dose IV or PO q12h |
|------------------|---------|------------------------------------|--|
| 2 – 11.99 years | all | IV: 9 mg/kg | IV: 8 mg/kg or PO: 9 mg/kg (max: 350 mg/dose) |
| 12 – 13.99 years | < 50 kg | IV: 9 mg/kg | IV: 8 mg/kg or PO: 9 mg/kg (max: 350 mg/dose) |
| 12 – 13.99 years | ≥ 50 kg | IV: 6 mg/kg | IV: 4 mg/kg or PO: 200 mg |
| ≥ 14 years | All | IV: 6 mg/kg | IV: 4 mg/kg or PO: 200 mg |

**All loading doses should be given IV q12h x 2 doses followed by either IV or PO maintenance dosing q12h.*

Centers that currently modify voriconazole prophylaxis dosing based on trough concentrations may continue this practice, and therefore may end up either exceeding the study recommended maximum dose listed above (if the trough is low) or be lower than the study recommended starting dose based on weight (if the trough is high). The actual dose administered and the reason for an adjustment to the study recommended dose will be recorded.

*For IV: The rate of infusion should not exceed 3 mg/kg/hour

Oral voriconazole is available as 50 and 200 mg tablets and as an oral suspension at a concentration of 40 mg/mL.

Rounding:

Tablets: Round the dose to the closest 50 mg.

Suspension: Round the volume to the closest tenth of a mL. Round 0.05 mL up (e.g., round 3.15 mL to 3.2 mL).

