Oral voriconazole is best taken 1 hour before or 1 hour after a meal. It should be administered at approximately the same times each day. If vomiting occurs within 30 minutes of taking the dose, the dose may be repeated once. If a dose is missed, it should be taken immediately and only if there are at least 12 hours until the next scheduled dose.

SEE SECTION 5.0 FOR DOSE MODIFICATIONS FOR TOXICITIES. For COG Supportive Care Guidelines see https://members.childrensoncologygroup.org/prot/reference_materials.asp

The therapy delivery map (TDM) for voriconazole prophylaxis is on the next page.

| | | |
|--|--------------------------------|-----------|
| 4.2.4 Voriconazole Treatment Arm. Patients randomized to voriconazole arm. | Patient name or initials _____ | DOB _____ |
|--|--------------------------------|-----------|

Prophylaxis with voriconazole begins within 24 hours of transplant (Day 0). Extensive administration details are in Section 4.2.3. This TDM is on One (1) page.

| DRUG | ROUTE | DOSAGE | DAYS | IMPORTANT NOTES | OBSERVATIONS |
|--------------|---|--|--|---|---|
| VORICONAZOLE | Slow IV infusion over 1-2 hours [#] (or longer) OR by mouth. | 2 - 11.99 years (all weights): LD IV: 9 mg/kg/dose MD IV: 8 mg/kg/dose or PO: 9 mg/kg/dose (max: 350 mg/dose) 12 – 13.99 years < 50 kg: LD IV: 9 mg/kg/dose MD IV: 8 mg/kg/dose or PO: 9 mg/kg/dose (max: 350 mg/dose) 12 – 13.99 years ≥ 50 kg: LD IV: 6 mg/kg/dose MD IV: 4 mg/kg/dose or PO: 200 mg/dose ≥ 14 years (all weights): LD IV: 6 mg/kg/dose MD IV: 4 mg/kg/dose or PO: 200 mg/dose | Twice daily Day 1 Day 2 (and subsequently) Day 1 Day 2 (and subsequently) Day 1 Day 2 (and subsequently) Day 1 Day 2 (and subsequently) | Start within 24 hours of transplant (Day 0). [#] For IV: The infusion rate should not exceed 3 mg/kg/hour | a. History, PE (ht, wt, BSA), albumin b. CBC, diff, plts, creatinine, AST, ALT, bilirubin c. GVHD Scoring d. IFI Checklist If patient consents: e. beta-D glucan testing (see Section 13) f. SNP (see Section 14) OBTAIN OTHER STUDIES AS REQUIRED FOR GOOD PATIENT CARE |

| Enter Date of Transplant Here | | Ht | cm | Wt | kg | BSA | m ² | |
|---|------------|----------------------------------|----|--|----|--------------------|--|--|
| Date Due | Date Given | Day | | VORICONAZOLE | | Studies | Comments (Include any held doses, or dose modifications) | |
| | | | | Day 1: _____ mg; Day 2 and Subsequently: _____ mg | | | | |

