| Unknown Frequency and Timing: | U.S. Food and Drug Administration's Pregnancy Category: Category D. Voriconazole can cause fetal harm when administered to a pregnant woman. Voriconazole was teratogenic in rats at doses 0.3 times the adult recommended dose and embryotoxic in rabbits at 6 times the recommended adult dose. Reduced fetal weight, skeletal abnormalities, and embryomortality were also reported in animal models. Additionally, plasma estradiol levels were reduced in pregnant rats at all dose levels of voriconazole. | | |

Formulation and Stability:

Injection

Voriconazole for injection is available in a single use vial as a sterile lyophilized powder without preservatives equivalent to 200 mg voriconazole and 3200 mg sulfobutyl ether beta-cyclodextrin sodium (SBECD). The powder for injection should be stored at 15°C to 30°C (59°F to 86°F). Reconstituted solutions are stable for up to 24 hours under refrigeration at 2°C to 8°C (36°F to 46°F).

Tablets

Voriconazole 50 mg tablets are white, film-coated, and round; voriconazole 200 mg tablets are white, film-coated, and capsule shaped. Both tablet types are debossed with “Pfizer” on one side and either “VOR50” or “VOR200” on the reverse, for the 50 mg and 200 mg tablets, respectively. Tablets should be stored at 15°C to 30°C (59°F to 86°F).

Powder for Oral Suspension

Voriconazole for Oral Suspension is supplied in 100 mL high density polyethylene (HDPE) bottles with an accompanying 5 mL oral dispenser and press-in bottle adaptor. Each bottle contains 45 g of powder for oral suspension. Following reconstitution, the bottle contains 40 mg voriconazole per mL in a usable volume of 70 mL and approximately 5 mL of overfill. The powder for oral suspension should be stored at 2°C to 8°C (36°F to 46°F). Once reconstituted, the oral suspension should be stored at 15°C to 30°C (59°F to 86°F).

Guidelines for Administration: See Treatment and Dose Modification sections of the protocol.

Powder for injection

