Aseptically reconstitute one 200 mg vial with 19 mL of sterile water for injection; the use of an automated syringe is not recommended. The resulting product is a clear, particle-free solution in a concentration of 10 mg/mL (20 mL total volume). This product should be further diluted with NS, LR, D₅WLR, D₅W^{1/2}NS, D₅W, D₅W with KCl 20 mEq, ^{1/2}NS, or D₅WNS to a final concentration of 0.5 to 5 mg/mL prior to administration. Do not dilute with 4.2% sodium bicarbonate infusion; slight degradation of voriconazole can occur.

Voriconazole powder for injection does not contain preservatives. The manufacturer recommends using the reconstituted solution immediately. Chemical and physical in-use stability has been demonstrated for 24 hours at 2°C to 8°C (36°F to 46°F). Any unused solution should be discarded. The final voriconazole solution should be infused over 1 to 2 hours at a rate not to exceed 3 mg/kg/hr.

Powder for oral suspension

A 40 mg/mL suspension is made by adding 46 mL of water to the powder in bottle. Shake well for approximately 60 seconds. Place the push-in bottle adaptor in place prior to dispensing to the patient. Prior to each dose, the bottle containing suspension should be shaken well for at least 10 seconds. Each dose should be withdrawn from the vial using the provided oral dose dispenser. Do not refrigerate or freeze. Discard any unused suspension 14 days after reconstitution.

Supplier: Commercially available product.

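### Section 6.3's closed 1 to 2 hour window for IV voriconazole cannot be met, under its own 3 mg/kg/h cap, for the 9 mg/kg loading dose or a full 8 mg/kg IV maintenance dose

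*Combined protocol and SAP*

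**What the plan says.** Three places in the combined protocol and SAP govern how IV voriconazole is infused.

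- **Section 6.3** (drug information, powder for injection), after the reconstitution and dilution steps: "The final voriconazole solution should be infused over 1 to 2 hours at a rate not to exceed 3 mg/kg/hr". The window is closed at 2 hours. Earlier in the same section a cross-reference reads: "Guidelines for Administration: See Treatment and Dose Modification sections of the protocol".
- **Section 4.2.3** (voriconazole comparator): slow infusion over 1-2 hours, followed by "or longer) OR by mouth", so the upper end is open. The cap is the same: "The rate of infusion should not exceed 3 mg/kg/hour".
- **The therapy delivery map (Section 4.2.4)**: the same open-ended window and the same cap.

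For ages 2 to 11.99 years at any weight, and for ages 12 to 13.99 years under 50 kg, the Section 4.2.3 table gives a 9 mg/kg IV loading dose and then maintenance of "IV: 8 mg/kg or PO: 9 mg/kg (max: 350 mg/dose". The delivery map repeats this: "LD IV: 9 mg/kg/dose MD IV: 8 mg/kg/dose or PO: 9 mg/kg/dose (max: 350 mg/dose". On route, Section 4.2.3 says: "All loading doses should be given IV q12h x 2 doses followed by either IV or PO maintenance dosing q12h". The remaining rows (ages 12 to 13.99 years at 50 kg or more, and 14 years and over) give 6 mg/kg IV loading and 4 mg/kg IV maintenance.

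**The concern.** The Section 6.3 sentence sets a duration and a rate limit together, and the two fix the largest dose that satisfies both. The doses ordered for the younger and lighter patients are larger than that. Someone preparing or giving the drug from Section 6.3 alone must break either the duration or the rate limit. If the duration is kept, the infusion runs faster than a limit that the protocol states three times. The patients concerned are the youngest on voriconazole, so this is an infusion-safety instruction and should be internally consistent.

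**Working it through.** **Inputs.** Rate cap r = 3 mg/kg/h (Sections 6.3 and 4.2.3, delivery map). Closed window of 1 to 2 h (Section 6.3). IV doses of 9, 8, 6 and 4 mg/kg (Section 4.2.3 table, repeated in the delivery map).

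**Step 1: largest dose that fits Section 6.3.** Window × cap = 2 h × 3 mg/kg/h = 6 mg/kg.

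**Step 2: shortest infusion time at the cap, and rate if given over 2 h.** Time = dose ÷ 3. Rate = dose ÷ 2.

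| IV dose | Use | Time at cap | Rate over 2 h | Share of cap | Fits within 2 h |
|---|---|---|---|---|---|
| 9 mg/kg | loading, younger rows | 9/3 = 3.0 h | 4.5 mg/kg/h | 4.5/3 = 150% | no |
| 8 mg/kg | IV maintenance, younger rows | 8/3 = 2.67 h | 4.0 mg/kg/h | 4.0/3 = 133% | no |
| 6 mg/kg | loading, older rows | 6/3 = 2.0 h | 3.0 mg/kg/h | 100% | yes, exactly |
| 4 mg/kg | IV maintenance, older rows | 4/3 = 1.33 h | 2.0 mg/kg/h | 67% | yes |

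The Section 6.3 window is therefore consistent with the 6 and 4 mg/kg rows and inconsistent with the 9 and 8 mg/kg rows.

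**Step 3: how far the conflict reaches.**

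- *Loading.* Both loading doses are IV, and no milligram maximum is printed against them. The conflict holds at every weight in the affected rows.
- *Maintenance.* It may be oral, and centers that already adjust on trough levels may continue, so the conflict needs an IV dose at the full 8 mg/kg. The 350 mg maximum is printed after the oral dose, and the table does not make clear whether it also covers the IV dose. If it does, the dose per kg starts to fall above 350/8 = 43.75 kg and reaches 6 mg/kg at 350/6 = 58.3 kg. At 60 kg it is 350/60 = 5.83 mg/kg, or 5.83/3 = 1.94 h, which fits. At 50 kg it is 350/50 = 7 mg/kg, or 7/3 = 2.33 h, which does not. On that reading only children under 12 weighing about 58.3 kg or more escape the maintenance conflict; the 12 to 13.99 year row under 50 kg does not.

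**Step 4: the same check on the other two places.** With the upper end open, 3.0, 2.67, 2.0 and 1.33 h are all permitted and the cap can be met at every listed dose. The contradiction comes only from the closed window in Section 6.3.

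**The case against.** The strongest reply is that the controlling text already handles this. Section 6.3 sends the reader to the treatment sections for administration, and there the window is open-ended. The cap has the same value in all three places, including inside the Section 6.3 sentence itself, so a site that puts the rate limit first never exceeds it. On this view, all that is missing is two words in one monograph sentence.

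Much of that stands. The documents never disagree on the rate limit, and a site working from Section 4.2.3 has a workable instruction. But Section 6.3 does not stop at the cross-reference. It goes on to give its own complete infusion instruction, which cannot be followed for a loading dose that the protocol orders.

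A reader might infer more than the documents support:

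- *That every weight-based IV dose in minors conflicts.* The 6 and 4 mg/kg doses are also weight-based and fit within 2 h.
- *That the 1 hour end is a further error because it exceeds the cap at every dose.* A range combined with a ceiling simply leaves the part of the range that respects the ceiling.
- *That about 140 patients are affected.* Section 9.3.4 expects about half of patients to have voriconazole as comparator, about 140 per arm. That is the whole voriconazole group at all ages, including those on 6 and 4 mg/kg.
- *That faster infusion would cause toxicity, removal from therapy and a distorted caspofungin-azole comparison.* Nothing in the documents links infusion rate to toxicity, and the primary analysis is by intention to treat, so removal from therapy does not itself remove a patient.

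**Conclusion.** The contradiction is real and narrow. As written, Section 6.3 cannot be followed for the two 9 mg/kg IV loading doses at ages 2 to 11.99 years, or at ages 12 to 13.99 years under 50 kg. It also cannot be followed when these patients receive IV maintenance at the full 8 mg/kg. A site that kept to 2 hours would run at one and a half times the stated cap for loading and one and a third times for maintenance.

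The loading-dose result assumes only that the doses are given as tabulated. The maintenance result also depends on route, on trough adjustment and on how the 350 mg maximum is read. The number of affected patients is not known.

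The severity is minor to moderate: a safety-relevant inconsistency in wording. It does not make the treatment plan unworkable, and no claim is made about bias in the treatment comparison.

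**What to change.** The sponsor should reconcile Section 6.3, Section 4.2.3 and the voriconazole delivery map so that infusion duration, rate limit and dose agree in all three. The same edit should make clear whether the 350 mg maximum covers IV maintenance, because that decides whether heavier children are affected. Which duration, rate or dose is clinically right is the sponsor's decision, and none is proposed here.

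The cost is a wording amendment in up to three places. It needs no new data and no change to the sample size or the analysis.

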7.0 REQUIRED OBSERVATIONS/MATERIAL AND DATA TO BE ACCESSIONED

Timing of protocol therapy administration, response assessment studies, and surgical interventions are based on schedules derived from the experimental design or on established standards of care. Minor unavoidable departures (up to 72 hours) from protocol directed therapy and/or disease evaluations (and up to 1 week for surgery) for valid clinical, patient and family logistical, or facility, procedure and/or anesthesia scheduling issues are acceptable per COG administrative Policy 5.14 (except where explicitly prohibited within the protocol).

7.1 Required and Optional Clinical, Laboratory and Disease Evaluations

All baseline studies must be performed prior to starting protocol therapy unless otherwise indicated below. These studies should be obtained even if the patient has been removed from protocol therapy, unless they are off study (see Section 8.0).

| STUDIES TO BE OBTAINED | Baseline | Day 0 to Day 42 (or Discharge) | Day 100^ End of ACCL1131 Monitoring |
|---------------------------------------|----------|-----------------------------------|---|
| REQUIRED | | | |
| CBC, differential, platelets | X | Twice Weekly | X |
| Performance Status | X | | X |
| Creatinine, AST, ALT, bilirubin | X | Twice Weekly | X |
| Albumin | X | Weekly | X |
| IFI checklist | | X* | X* |
| GVHD Scoring | | Weekly(after Day 14) | X |
| OPTIONAL (IF PATIENT CONSENTS) | | | |
| Beta-D Glucan Assays | | Weekly@ | |
| Sample for SNP Genotyping | X# | | X# |

^Day 100-114

*Submit relevant IFI checklist documents via the Document Imaging System: [contact] as of Day 42 and Day 100. See Section 10.2 for further details.

@ See Section 13 for details. It is suggested that specimens be obtained on Thursdays but other days are acceptable if more convenient. During the prophylaxis period, documentation of exposure or lack of exposure to each of the following will be performed: amoxicillin-clavulanate and intravenous immunoglobulin.

See Section 14 for details. End of study sample may be collected on Day +100 +/-7 days.

This table only includes evaluations necessary to answer the primary and secondary aims. Obtain other studies as indicated for good clinical care.

7.1.1 History, Demographic and Clinical Information

Demographic and clinical information collected at baseline will include age, sex, performance status, Down syndrome, ethnicity, height, weight, and episodes of fully-treated proven/probable yeast infection in the 3 months prior and receipt of systemic antifungal therapy within 7 days prior to enrollment. Other information collected will include type of malignancy or underlying diagnosis, relapse status, donor type, degree of donor match, stem cell source, conditioning regimen and graft-versus-host disease (GVHD) prophylaxis.

7.2 **Optional Studies**

7.2.1 (1→3) Beta-D Glucan Assays

If patient consent is obtained, Fungitell beta-D-glucan Assay will be performed during the period of neutropenia in order to identify IFI. 5 mL of whole blood will be collected in a gold top serum-separator tube once weekly. See Section 13 for sample collection, processing and shipping details.

7.2.2 SNP Analysis

If patient consent is obtained, specimens will be collected and banked for genotyping. SNP analysis will be conducted in order to determine genes mediating immune function. Peripheral blood (5 mL) will be collected in a purple top tube at study entry and at end of study (Day +100 +/-7 days), optimally when the patient has an ANC > 1000/ μ L. Patients with weights less than 20 kg may have only 3 mL collected. See Section 14 for sample collection and shipping details.

7.3 **Follow-up**

See COG Late Effects Guidelines for recommended post treatment follow-up
<http://www.childrensoncologygroup.org/disc/LE/default.htm>

8.0 **CRITERIA FOR REMOVAL FROM PROTOCOL THERAPY AND OFF STUDY CRITERIA**

8.1 **Criteria for Removal from Protocol Therapy**

- a) Development of proven or probable IFI including IA according to the institutional diagnosis.
- b) Refusal of further protocol therapy by patient/parent/guardian.
- c) Completion of planned therapy (Day 42 or Day of Discharge).
- d) Physician determines it is in patient's best interest.
- e) Repeat eligibility studies are outside the parameters required for eligibility (if applicable, see Section 3.2 – only for patients that have not yet started protocol therapy).
- f) Intolerable toxicities as outlined in Section 5.2 and Section 5.3.

Patients who are off protocol therapy are to be followed until they meet the criteria for Off Study (see below). Follow-up data (including IFI checklist) will be required unless consent was withdrawn.

8.2 **Off Study Criteria**

- a) Death.
- b) Lost to follow-up.
- c) Withdrawal of consent for any further data submission.
- d) Completion of Day 100 evaluation.

9.0 STATISTICAL CONSIDERATIONS

9.1 Statistical Design

This is a randomized open-label trial of anti-fungal prophylaxis for patients at high risk for IFI following allogeneic hematopoietic cell transplantation. Eligible patients are those undergoing an allogeneic HCT from an unrelated donor or mismatched family donor. Patients will be randomized at the time of enrollment to receive caspofungin or an azole comparator (fluconazole or voriconazole). Each participating institution will choose the comparator based upon institution standard of care and the choice of comparator should remain constant for the duration of the study. Randomization will be stratified by: 1) the comparator of choice: fluconazole or voriconazole; 2) Age: ≥ 12 years vs. < 12 years; 3) Type of transplant: Umbilical cord blood (UCB) donor vs. Non-UCB donor with ex vivo T-cell-depletion vs. Non-UCB donor with standard pharmacologic GVHD prophylaxis. Protocol-specified anti-fungal prophylaxis will start with 24 hours of Day 0 and continue until Day +42, day of discharge, or withdrawal from study for any reason. The primary aim of the study is to evaluate whether the caspofungin arm has a lower incidence of proven/probable IFI than the azole arm during the first 42 days following allogeneic HCT.

9.2 Patient Accrual and Expected Duration of Trial

In North America, from 2006-2008, an average of 688 patients per year were transplanted at COG centers that fit the eligibility criteria for this trial (CIBMTR, personal communication). Presuming constant numbers and a 20% participation rate, this trial would accrue about 138 patients per year and require 4.5-5 years (including an estimated 6 months delay for IRB approvals) to complete the accrual of 560 eligible patients, with a maximum enrollment of 590 patients to account for up to 5% ineligible enrollments. Because we will allow institutions to choose the comparator (fluconazole or voriconazole), we anticipate a high acceptance of this trial by local physicians, and indeed, our survey of the COG Transplant Centers indicated that 89% of the centers who responded would enroll patients on this trial, with a survey response rate of 80%.

9.3 Statistical Analysis Methods

9.3.1 Study Endpoints

Primary endpoint

The primary endpoint is the development of proven or probable IFI defined according to criteria developed by the European Organization for Research and Treatment of Cancer/Mycoses Study Group (EORTC/MSG) (from which time to IFI will be computed).³¹ These definitions have been used in major trials of antifungal drug efficacy, in strategy trials, for formulating clinical practice guidelines, for validating diagnostic tests, as well as for undertaking epidemiologic studies. A Data Review Committee, blinded to study drug assignment, will review all clinical documentation used to determine the presence of an IFI and classify it based on the EORTC criteria. The period at risk for primary IFI endpoint will begin at Day 0 and extend until 42 days following stem cell infusion. Some patients at high-risk for IFI may have prolonged inpatient stays, but in order to obtain a relatively homogenous duration of study drug administration, Day +42 was chosen as the maximal period of administration, as was done in the micafungin trial. Based on intent-to-treat principle, the at-risk period will be the same for patients who terminated protocol prophylaxis prior to Day +42 (due to withdrawal or discharge) as long as data regarding IFI are available. For the primary endpoint, deaths that occur in the absence of proven/probable IFI will be counted as censoring events; as a comparison, for the exploratory endpoint of fungal-free-survival (see below), deaths without proven/probable IFI will be counted as events.

The rationale for the duration of therapy and the measurement of the primary endpoint was based upon three issues. First, the major time period that patients are at risk for invasive candidiasis is during the period of combined neutropenia, monocytopenia, and lymphopenia.⁵³ The second reason is that this time frame was the same as was used in the NIAID-supported micafungin trial by Van Burik *et al.*, and thus, allows us to compare our results to what was seen in that lower-risk, primarily-adult population.¹⁴ The final issue was one of feasibility. The goal was to design a trial that would not mandate a practice that is not standard to local institutions, namely continuing an intravenous medication past the time of hospital discharge, when an acceptable oral medication exists. It was felt that this burden would potentially represent a serious obstacle to widespread acceptance and participation in the trial. This pragmatic trial is designed to determine whether the intervention works under the usual circumstances in which it is used. Once the period of neutropenia and monocytopenia has resolved many patients will be clinically ready for discharge from the hospital. Since caspofungin is only available in an intravenous formulation, continuing the treatment past the time of discharge represents a significant burden of effort and cost, which the data currently do not support undertaking.

Exploratory Endpoints

Endpoints for the exploratory objectives include: development of proven or probable IFI during the first 100 days following allogeneic HCT, fungal-free-survival which is defined as time to death or proven/probable IFI during the first 42 and 100 days following allogeneic HCT, and onset and severity of acute GVHD, and results from beta-D glucan assay for the diagnosis of IFI.

